12.3.1 Analysis Population

All Treated Subjects: All subjects who received at least one dose of pembrolizumab and completed the prescribed course of palliative radiation therapy.

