4. TREATMENT PLAN

Screening/Baseline Visit

The following tests and examinations must be performed and the eligibility criteria satisfied before treatment may begin:

- Histologic diagnosis of Merkel Cell Carcinoma
- Demographics and medical history
- Measurements of weight, height, temperature, pulse, respiratory rate, and resting systolic and diastolic blood pressure
- Complete physical examination
- ECOG Performance Status
- Clinical laboratory tests:
 - Hematology: hemoglobin, hematocrit, CBC counts with differential (including absolute lymphocyte count) and direct platelet count
 - Serum Chemistry: albumin, serum alkaline phosphatase, SGOT (AST)/SGPT (ALT), total bilirubin, calcium, creatinine, glucose, lactate dehydrogenase (LDH), total protein, urea nitrogen (BUN), electrolytes (including sodium, potassium, chloride, and bicarbonate), TSH w/Reflex FT4
 - Urinalysis:
 - Gross examination including specific gravity, protein, glucose, and blood
 - Optional microscopic examination including WBC/HPF, RBC/HPF and any additional findings
- Optional Blood sample obtained for investigational immune response assays
- Chest radiography unless baseline CT scan was performed
- Electrocardiogram
- Relevant baseline radiographic images (e.g. brain, chest, abdomen, pelvis, and bone scans with the exact imaging studies utilized determined by the attending physician) within 6 weeks of initiation of anti-PD-1/PD-L1

- Current medications
- Baseline review of symptoms
- Pregnancy test
- Optional Tumor biopsy

Treatment Visits

The day subjects receive the first dose of pembrolizumab therapy will define Day 1. Subjects are required to have blood collected and chemistry labs analyzed up to 1 week prior to each dose of pembrolizumab. Investigators or an assigned medical professional must review liver function tests from the predosing labs and ensure the results meet dosing requirements prior to authorizing administration of each dose of pembrolizumab.

Subjects will receive a single dose of pembrolizumab as standard of care with 200mg IV every 3 weeks (with a -3 and +7-days window) until disease progression or unacceptable toxicity occurs.

During this treatment phase, the following procedures will be performed within 1 week of each scheduled visit:

- Pregnancy test for WOCBP, required within 6 weeks before first dose of pembrolizumab, then optional as clinically indicated for ongoing doses

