5.1.2 Radiation Therapy

Patients will receive palliative radiation therapy to 1-2 sites of disease. Radiation therapy will be delivered between the first and second cycles of anti-PD-1/PD-L1 therapy. The total dose and fractionation regimen of radiation will be determined by the attending physician by such factors as the location and size of the lesion that requires radiation, volume of radiosensitive normal tissue in the field, and clinical status of the patient. Patients will be treated with either 9 Gy X 3 (27 Gy in 3 fractions), or 4-6 Gy X 5 (20-30 Gy in 5 fractions). Radiation therapy will be planned in 3 or 4 D, and may be delivered using conventional, IMRT/ rapid arc or SBRT. Portal imaging for QC will occur according to SOC. All patients will be seen at least weekly by the attending physician while on treatment.

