7.2 Adverse Event Reporting

Adverse events will be graded according to CTCAE v5.0. Both Serious and Non-Serious Adverse Events will be clearly noted in source documentation and listed on study specific Case Report Forms (CRFs). The Protocol Director or designee will assess each Adverse Event (AE) to determine whether it is unexpected according to the Informed Consent, Protocol Document, or Investigator’s Brochure, and related to the investigation. All Serious Adverse Events (SAEs) will be tracked until resolution or until 60 days after the last dose of the study treatment. Immune related serious adverse events (irSAEs) definitely related to study treatment will be captured for 6 months after the last dose of study treatment.

SAEs CTCAE Grade 3 and above, and all subsequent follow-up reports will be reported to the Stanford Cancer Institute Data and Safety Monitoring Committee (DSMC) using the study specific CRF regardless of the event’s relatedness to the investigation. Following review by the DSMC, events meeting the IRB definition of ‘Unanticipated Problem’ will be reported to the IRB using eProtocol within 10 working days of DSMC review, or within 5 working days for deaths or life-threatening experiences.

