f: If funding is available, a variety of optional immune response assays will be performed that may include Luminex for 51 cytokines testing in serum or plasma, ELISA for MHC class 1 polypeptide-related sequence A (MYCA) and MHC class 1 polypeptide-related sequence B (MYCB) in serum or plasma, immunophenotyping including myeloid-derived suppressor cells (MDSC) and gamma/delta T cells, mass cytometry or CyTOF ICS with phorbol 12-myristate 13-acetate (PMA) + ionomycin stimulation (global immunocompetence assay). These assays will be performed at baseline, 2 weeks (± 1 weeks) and 8 weeks (± 1 weeks) after radiation therapy. Possible tumor biopsies (optional) may be performed before, during/after treatment to assess response to therapy and changes in immune cell subsets. Optional tests to assess polyomavirus in the blood may be performed at baseline and 3 months ± 1 month.

g: Applicable to all subjects who discontinued, regardless of enrollment date. During the Survival Follow-Up Phase, telephone contact will be made every 6 months (± 2 weeks) for 5 years from the last dose of pembrolizumab. The site will inquire about overall subject survival status. Subjects that withdraw from the treatment phase of the study but do not return to the site for any further assessment will be contacted by the site to inquire about AEs and SAEs up to at least 60 days from the last dose of pembrolizumab. Definitely related immune related serious adverse events (irSAEs) will be captured for 6 months after the last dose of study treatment.

h: Required before first dose of pembrolizumab

1. If systemic steroids are required, subjects should be stable on the lowest clinically effective dose (≤ 20 mg/day)

2. Must be at least 14 days since treatment for MCC, and recovered (baseline or residual non ir Grade 1 toxicity or ir Grade 2 toxicity at the investigator's discretion, see section 4.1.1) from any clinically significant toxicity experienced during treatment before the first dose of on study pembrolizumab therapy.
3. ≤ 6 weeks demonstrate measurable disease according to RECIST v1.1, and have baseline (screening/baseline) radiographic images, (e.g. CT, PET CT or MRI brain, chest, abdomen, pelvis, to be determined by the attending physician)
4. ≤ 6 weeks pregnancy test for WOCBP
5. ≤ 1 week labs and liver function tests performed and results evaluated

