10.1.2.9 Survival

Survival is defined as the duration of time from study entry to time of death or the date of last contact.

10.1.3 irRECIST

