12. STATISTICAL CONSIDERATIONS

12.1 Statistical Design

This is a single arm non-randomized open trial to determine the response rate for patients who are treated with both pembrolizumab and palliative radiation therapy.

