12.3.2 Analysis Plan

Data will be summarized using appropriate descriptive statistics: proportions with Wilson’s 95% confidence intervals, means, standard deviations, ranges, and Kaplan-Meier estimates for time to event data. The toxicity rates will be monitored continuously and a final count of toxicities will be performed.

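### The only analysis set, labelled 'All Treated Subjects', requires completed radiation: dosed patients who stop earlier drop out of response and OS, and the toxicity rates have no stated denominator

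*Combined protocol and SAP*

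**What the plan says.** For the primary analysis, section 12.3.1 calls its population 'All Treated Subjects' and defines it as "All subjects who received at least one dose of pembrolizumab and completed the prescribed course of palliative radiation therapy". Section 12.4.1 gives the same definition for the secondary analyses. Section 12 defines no enrolled, intention-to-treat or safety set and gives no replacement rule. This one set therefore governs the complete response rate (12.3) and the response rate, OS and duration of response (12.4).

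Three other passages fix the timing:

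- Section 5.1.2: "Radiation therapy will be delivered between the first and second cycles of anti-PD-1/PD-L1 therapy".
- Section 4, on the pembrolizumab schedule: "every 3 weeks (with a -3 and +7-days window".
- Section 10.1.2.9: "Survival is defined as the duration of time from study entry to time of death or the date of last contact".

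The aim in 12.1 is "to determine the response rate for patients who are treated with both pembrolizumab and palliative radiation therapy". Section 1.1 lists safety first of its two primary objectives. On the analysis of safety, 12.3.2 and 12.4.2 say only this: "The toxicity rates will be monitored continuously and a final count of toxicities will be performed".

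**The concern.** Membership of the set depends on something that happens after treatment has started. A patient who receives dose 1 and then dies, deteriorates or withdraws before the last radiation fraction has been treated but is not in 'All Treated Subjects'. A patient who finishes radiation and then stops pembrolizumab stays in. The two kinds of early stopper are handled differently, and the label does not show it.

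This has three consequences. First, OS time runs from study entry while membership is earned later, so every analysed patient is certain to survive to the end of radiation (immortal time). Second, the denominator of both response rates excludes patients who could not complete the combination. Third, toxicity rates have no stated denominator. Section 6 counts permanent discontinuation for toxicity, and withdrawal for toxicity the patient finds unacceptable, as dose-limiting. Some of these patients may stop before radiation ends, and a completer denominator would lose them from the result for a primary objective.

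**Working it through.** **1. The plan's own figures.** The Wilson 95% limits are [p + z²/2n ± z√(p(1−p)/n + z²/4n²)] / (1 + z²/n), with z = 1.96. For 6/30 this gives 9.51% to 37.31%, matching the 9.5% and 37.3% in 12.5. The half-width is at most 15.5% for 0 to 8 responders (and for 22 to 30, which adds a negligible amount). The Binomial(30, 0.20) probability of those counts is 0.8713, matching the stated 87%. The sample-size arithmetic is sound.

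**2. Length of the immortal period.** With dose 2 inside its window, the interval from dose 1 is 21 − 3 = 18 days to 21 + 7 = 28 days. Radiation ends within it. Any time from study entry to dose 1 is added.

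**3. Early OS.** The documents give no early death rate. Assume 1 or 2 of 30 dosed patients die before radiation ends. Survival at that point is 29/30 = 96.7% or 28/30 = 93.3%, but the completer set shows 100% by construction. The later direction also depends on how excluded patients who were still alive fare, which the documents do not tell us. The upward bias is therefore claimed only for the early part of the curve.

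**4. Response.** The documents give no radiation non-completion rate. Assume m = 1 to 5 of 30 dosed patients do not finish and r of these respond. With R responders in all, the completer set reports (R − r)/(30 − m) instead of R/30. If r = 0, the inflation factor is 30/(30 − m), whatever R is, so it applies equally to complete response and to overall response. For R = 6:

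| m | r = 0 (Wilson 95% CI) | r = 1 |
|---|---|---|
| 0 | 6/30 = 20.0% (9.5% to 37.3%) | – |
| 1 | 6/29 = 20.7% (9.8% to 38.4%) | 5/29 = 17.2% |
| 2 | 6/28 = 21.4% (10.2% to 39.5%) | 5/28 = 17.9% |
| 3 | 6/27 = 22.2% (10.6% to 40.8%) | 5/27 = 18.5% |
| 4 | 6/26 = 23.1% (11.0% to 42.1%) | 5/26 = 19.2% |
| 5 | 6/25 = 24.0% (11.5% to 43.4%) | 5/25 = 20.0% |

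The rate is inflated only when r/m is below R/30. With r = 0 the shift is 0.7 to 4.0 points, against an interval 37.3 − 9.5 = 27.8 points wide. With r = 1 the shift is downward, or nil at m = 5.

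**5. Precision, if the 30 in 12.5 are dosed patients.** At a 20% rate, the probability of a half-width of at most 15.5% is 87.1% at n = 30, 79.0% at 29, 81.8% at 28, 71.3% at 27, 57.7% at 26 and 61.7% at 25. It is not monotone because the binomial is discrete.

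**6. Toxicity, if the completer set were the denominator.** Assume 4 of 30 dosed patients have a dose-limiting toxicity (13.3%, close to the 14% discontinuation for treatment-related events that section 2.2 cites for pembrolizumab alone). If one of the four stops before finishing radiation, the rate reads 3/29 = 10.3%. If two do, it reads 2/28 = 7.1%.

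**The case against.** The strongest defence is that 12.1 aims at patients treated with both modalities and 1.1 asks for response at irradiated sites. In a descriptive single-arm study with no hypothesis test, a set of patients who received the combination fits that aim, and the label is defined where it is used. This stands as a reason to report completers. It does not justify reporting only completers, or naming them as if they were everyone treated.

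The effect is also likely to be small. Radiation is 3 to 5 treatments (7.1.2), eligibility requires a life expectancy of at least 16 weeks (3.1.5), and OS is secondary. This stands too.

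A reader might infer two stronger points, and the documents support neither.

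- *The response rate is overstated.* Unfinished radiation is not among the reasons for mandatory discontinuation in 4.2 or 5.1.1.3, so a non-completer may continue pembrolizumab. Section 2.2 cites a 56% response rate for pembrolizumab alone in patients without prior systemic therapy. Non-completers may therefore respond, and the direction is open.
- *Toxicities in non-completers will be discarded.* Nothing says so. Monitoring is continuous, the calendar starts adverse event evaluation at Week 1, and under 7.2 "SAEs CTCAE Grade 3 and above, and all subsequent follow-up reports will be reported to the Stanford Cancer Institute" monitoring committee regardless of relatedness. Under note g of the calendar, patients who withdraw from treatment and do not return "will be contacted by the site to inquire about AEs and SAEs up to at least 60 days from the last dose of pembrolizumab". What is missing is a stated denominator. That the completer set would serve is only an inference from where the toxicity sentence sits.

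**Conclusion.** The point holds in a limited form and should be fixed. As written, dosed patients who do not finish radiation are outside every efficacy analysis, under a label that suggests otherwise.

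Early OS is biased upward by construction if any such patient dies before radiation ends. The period is short, and the 96.7% and 93.3% rest on an assumed 1 or 2 deaths. Response may be overstated by up to 4.0 points, unchanged or understated, under an assumed 1 to 5 non-completers of 30. That is small beside the planned interval.

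The toxicity gap carries the most weight because safety is a primary objective. It is an unspecified denominator, not a shown exclusion. The figures planned in 12.5 are correct, but the plan does not say whether its 30 are dosed patients or completers.

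**What to change.** - Define an all-dosed set: every patient with at least one on-study pembrolizumab dose. Name it as the denominator for toxicity rates in 12.3.2 and 12.4.2, and use it for OS from study entry.
- Report the complete response rate and the overall response rate in that set. Patients with a scan are scored by their overall response whether or not radiation was finished. Those with no post-baseline assessment count as non-responders.
- Rename the present set 'radiation completers' and report it alongside, for the question in 12.1. Report irradiated-site response among irradiated patients only.
- If OS is shown for completers, start it at the end of radiation and record this as an exception to 10.1.2.9.
- Report how many patients did not finish radiation, and why.
- State which set the 15 in 12.2 and the 30 in 12.5 refer to.

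The cost is wording in section 12, with a note at 10.1.2.9 if completers' OS is shown. No new procedure is needed: adverse events are already collected from Week 1, and section 4 plans survival contact, where possible, for all enrolled subjects.

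There are drawbacks. The reported response rate may be slightly lower. The all-dosed result will include any responses to pembrolizumab without completed radiation, which is why the completer result stays beside it. Some early stoppers will have no scan, because 4.2 exempts those who withdraw consent for all procedures and 5.1.1.3 waives the visit for those switched to another anti-cancer drug. The all-dosed set still conditions on reaching dose 1, so any time between entry and that dose remains event-free.

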12.3.2 Analysis Plan

Data will be summarized using appropriate descriptive statistics: proportions with Wilson’s 95% confidence intervals, means, standard deviations, ranges, and Kaplan-Meier estimates for time to event data. The toxicity rates will be monitored continuously and a final count of toxicities will be performed.

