1. OBJECTIVES

1.1. Primary Objective

The primary objectives of this study are to assess 1) the safety and 2) efficacy of combining Anti-PD-1/PD-L1 blockade with palliative radiation therapy in patients with Stage IV Merkel Cell Carcinoma. Efficacy for the primary objective will be tumor response rates (CR, PR, SD, irCR, irPR, irSD) at both irradiated and unirradiated sites.

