2.3 Rationale

The underlying hypothesis for this study is that local radiation therapy (RT) can be safely used in combination with PD-1/PD-L1 blockade. This combination therapy may have the potential

to enhance the induction of systemic anti-Merkel cell carcinoma immune responses, which will inhibit growth and kill Merkel cell tumor cells in sites of established metastases outside of the local radiation therapy field.

This is a single institution study of pembrolizumab combined with palliative radiation therapy in patients with metastatic Merkel cell carcinoma. Palliative treatment means treatment to shrink a tumor, slow its growth or control symptoms. Patients must require radiation therapy for palliation of symptoms or to prevent local progression of disease and associated complications and/or symptoms from metastases.

Radiation therapy (RT) is commonly used to palliate sites of metastatic disease. Radiation can locally kill Merkel carcinoma cells and result in the release of tumor antigens in close proximity to antigen presenting cells (APC) in tumors, which could help to initiate an anti-tumor immune response. The combination of RT with PD-1/PD-L1 blockade, which inhibits co-inhibitory signaling in between T cells and tumor, may result in enhanced anti-tumor responses that result in greater tumor burden reduction systemically.

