	For any of the following: Life-threatening adverse reaction (excluding endocrinopathies) Recurrent severe immune-mediated adverse reaction Requirement for 10 mg per day or greater prednisone or equivalent for more than 12 weeks Persistent Grade 2 or 3 immune-mediate adverse reactions lasting 12 weeks or longer	Permanently discontinue.
Infusion-related reaction	Grade 1 or 2	Interrupt or slow the rate of infusion.
	Grade 3 or 4	Permanently discontinue.

*Toxicity was graded per National Cancer Institute Common Terminology Criteria for Adverse Events. Version 5.0 (NCI CTCAE V5)

(a) Resume if complete or partial resolution (Grade 0, 1) after corticosteroid taper.

Dose Limiting Toxicity (DLT) Definition:

Dose limiting toxicity is when therapy is permanently discontinued due to toxicity as defined in the dose modification table above or when the patient withdraws from treatment due to toxicity that the patient finds unacceptable.

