12.3 Primary Analysis

Primary Endpoint: The determination of the complete response rate and the 95%CI using Wilson’s method

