12.4 Secondary Analysis

Secondary endpoints: Response rate, overall survival, and duration of response (please see section 10.1).

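### Safety is the first primary objective, but Section 12 names no safety endpoint, and its only analysis population leaves out patients whose toxicity stopped radiation

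*Combined protocol and SAP*

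**What the plan says.** - **Objective (1.1):** "The primary objectives of this study are to assess 1) the safety and 2) efficacy" of the combination.
- **Hypothesis (2.3):** "local radiation therapy (RT) can be safely used in combination with PD-1/PD-L1 blockade".
- **Primary endpoint (12.3):** "The determination of the complete response rate and the 95%CI using" Wilson's method.
- **Secondary endpoints (12.4):** "Secondary endpoints: Response rate, overall survival, and duration of response". Neither list contains a safety endpoint. Section 10 states that its listed outcome does not measure safety and leaves safety to CTCAE v5.0 adverse event assessment.
- **Safety analysis (12.3.2, repeated in 12.4.2):** "The toxicity rates will be monitored continuously and a final count of toxicities will be performed". The preceding sentence gives Wilson 95% intervals for proportions in general.
- **Analysis population (12.3.1, repeated in 12.4.1):** patients with at least one pembrolizumab dose who also "completed the prescribed course of palliative radiation therapy". No separate safety population is defined.
- **DLT (Section 6):** the first limb reads "Dose limiting toxicity is when therapy is permanently discontinued due to toxicity as defined in the dose modification table above", and that table covers pembrolizumab only. A second limb adds a patient's own withdrawal from treatment for toxicity that he or she finds unacceptable. Section 2.4 also uses the term, in treatment guidance, and explains it by the example of serious adverse events. Sections 10 to 12 do not use it.

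**The concern.** A primary objective should lead to a defined quantity, in a defined set of patients, with a stated precision. For safety, the plan gives an activity (monitoring) and a tally. It does not say which event is counted, over what period, or per patient or per event.

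The population makes this more than a matter of drafting. The hypothesis concerns radiation given with PD-1 blockade, and patients who could not finish radiation because of toxicity are among the most informative about it. Applied as written, the population rule in 12.3.1 removes them from the safety result. A reader of the final report could then see a toxicity rate that looks more favourable than the rate among patients treated.

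The DLT definition, the natural candidate for an endpoint, also has a gap. If a physician stops radiation for toxicity, and the patient neither withdraws nor permanently stops pembrolizumab, neither limb is met.

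**Working it through.** **1. The plan's own figures.** Section 12.5 gives a Wilson interval of 9.5% to 37.3% for an observed 20% in 30 patients, and 87% power for a half-width of 15.5%. With p the observed proportion, n the number of patients and z = 1.96:

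- centre = (p + z²/2n) / (1 + z²/n)
- half-width = z √(p(1−p)/n + z²/4n²) / (1 + z²/n)

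For 6/30, the centre is (0.2000 + 0.0640)/1.1280 = 0.2341 and the half-width is 1.96 × 0.0800/1.1280 = 0.1390, giving 9.5% to 37.3%. The half-width is at most 15.5% when X ≤ 8, and P(X ≤ 8 | n = 30, p = 0.20) = 0.871. Both figures reproduce, but they concern response. The documents give no safety figure to reproduce.

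**2. Effect of the population rule.** Assume 6 of 30 treated patients have a qualifying toxicity, and d of those six did not complete radiation because of it. The analysed result is (6 − d)/(30 − d):

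| d | Analysed | Rate | Wilson 95% CI |
|---|---|---|---|
| 0 | 6/30 | 20.0% | 9.5% to 37.3% |
| 1 | 5/29 | 17.2% | 7.6% to 34.5% |
| 2 | 4/28 | 14.3% | 5.7% to 31.5% |
| 3 | 3/27 | 11.1% | 3.9% to 28.1% |

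At d = 3 the estimate falls by 20.0 − 11.1 = 8.9 percentage points and the upper limit by 37.3 − 28.1 = 9.2 points. Patients who miss radiation for unrelated reasons and have no event also leave. Three of those alone would give 6/27 = 22.2%, a move in the other direction. The downward bias is specific to toxicity that stops radiation.

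**3. Continuous monitoring.** No reference rate or rule is given, so its properties cannot be computed. For scale, take 14% as an assumed reference: Section 2.2 reports that 14% of 50 patients on pembrolizumab alone stopped for treatment-related events (7/50, Wilson 7.0% to 26.2%). Testing after each of 30 patients at an unadjusted one-sided 5% raises a false alarm with probability 12.1%.

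An illustrative alternative uses a Beta(0.28, 1.72) prior, whose mean is 0.28/2.00 = 14%. It pauses for review when the posterior probability that the rate exceeds 14% is at least 0.97, checked from patient 5. The rule is met at 3/5, 5/10, 6/15, 7/20, 8/25 and 9/30. Exact recursion over 30 patients gives:

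| True rate | P(pause) |
|---|---|
| 14% | 7.5% |
| 20% | 25.8% |
| 30% | 69.7% |
| 40% | 94.3% |

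**The case against.** The strongest reply is that safety is already overseen. Adverse events are graded by CTCAE v5.0, serious events of grade 3 and above go to the DSMC whatever their cause (7.2), the DSMC reviews serious events regularly (11.2), and Section 6 governs discontinuation for each patient. Both treatments are described as standard of care (5.2). All of this stands. Oversight is present; a defined safety result is not.

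A reader might infer more than the documents support:

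- **That toxicity ending radiation is never a DLT.** The second limb of Section 6 is not tied to the pembrolizumab table and can capture radiation toxicity if the patient withdraws. The gap is limited to the physician-stopped case above.
- **That toxicity carries no confidence interval.** The general Wilson wording in 12.3.2 can be read to cover toxicity proportions. What is missing is the event and the denominator.
- **That better safety rules would show that adding radiation is safe.** In a single-arm trial no rule can isolate radiation's contribution. It can only compare the combination with a stated rate.
- **That affected patients vanish from the record.** Adverse events are collected without regard to completion of radiation, and monitoring need not be limited to completers. The loss occurs in the analysis set.
- **That a numeric safety boundary is obligatory because futility has one (12.2).** Relying on DSMC judgement is a legitimate choice. The 14% reference is also not like for like: those patients were treatment-naive and on monotherapy, whereas this trial admits patients after progression on prior therapy (2.4), ECOG 0 to 2 (3.1.4), and possible prior PD-1/PD-L1 exposure (4.1.1). The expected rate could exceed 14% with no excess from the combination, and at a true 20% the illustrative rule pauses about one time in four.

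**Conclusion.** The point holds for the endpoint and the population. Section 12 gives the first primary objective no named endpoint, leaves the defined DLT unused, and restricts its analyses to radiation completers. Toxicity that stops radiation therefore leaves numerator and denominator, and the reported rate is biased downward. The size depends on how many events stop radiation, which the documents do not indicate. Under the assumed 6 events in 30, one to three such patients lower the estimate from 20.0% to between 17.2% and 11.1%. This assumes that 12.3.1 is applied literally to the toxicity analysis and that no other exclusions offset it.

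The documents do not support saying that safety goes unmonitored, or that a stopping boundary is required. The boundary is a trade-off for the sponsor and DSMC.

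**What to change.** **Recommended, in 12.3:**
1. Add a safety population: all patients who received at least one dose of pembrolizumab, whether or not radiation was completed. Because radiation falls between cycles 1 and 2, this covers everyone who starts it.
2. Name the safety endpoint: the proportion of patients with at least one DLT over a stated observation window, with the Wilson 95% interval already specified. The window matters because pembrolizumab continues until progression or toxicity.
3. For this analysis only, also count toxicity that ends radiation early.
4. Reconcile the descriptions of DLT in Sections 2.4 and 6. Which one applies is for the sponsor to settle.

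**Optional, in 12.2:** a numeric boundary for referral to the DSMC, with its reference rate, cut-off, window and exact operating characteristics stated. The sponsor and DSMC would choose these.

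**Cost:** items 1 to 4 are wording changes and alter no treatment rule. The reported toxicity rate may be less favourable. The population may include a few patients who had pembrolizumab but no radiation, and their number should be reported. The boundary costs more: in the illustration, a 7.5% chance of an unneeded pause if the true rate equals the reference, and 26% if the true rate is 20% for reasons unrelated to the combination.
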